Cover Page for ClinicalTrials.gov

Official Title of the Study:

Sex-specific Adaptation to Different Resistance Exercise Programs in Older Adults

Date of the document:

April 22, 2019

Objectives

The objectives of this study are to identify the sex-specific effects of low-velocity, high-load resistance training (RT) versus high-velocity, low-load power training (PT) on skeletal muscle function at the whole muscle, cellular and molecular levels in older adults.

Design

We will test our hypothesis by having healthy, sedentary older (65-75 years old) men and women exercise one leg using RT and the contralateral leg using PT, and examining muscle function from the molecular, cellular and whole muscle levels. This within subject, unilateral training design provides a powerful model to evaluate training differences by reducing between-subject variability. Unilateral exercise, with one leg exercised and the other as a control, has been commonly used in older populations to examine muscle gene expression to myofibrillar ultrastructure to whole muscle performance.

Methods

Recruitment. Healthy older (65-75 years) men and women will be recruited from Amherst, MA and surrounding areas. Using the 2010 census data, ~45,000 volunteers between the ages of 65-75 live within 25 miles of Amherst. The best evidence of our recruitment capacity in this area is the track record of members of the investigative team for conducting recent research studies in older adults and requiring multiple biopsies.

Pre-exercise testing (Baseline). Baseline testing will occur prior to exercise and include assessments of body composition, physical activity, and whole skeletal muscle to cellular and molecular function.

Body composition, physical activity and function: Body mass, total and regional body composition will be assessed by dual energy x-ray absorptiometry (DEXA) (2); knee extensor fat content (% total) and fat-free muscle mass by magnetic resonance imaging (MRI); and 7 days of free-living physical activity by Actigraph GT3X-BT monitor. Physical activity will be matched across sex groups to reduce this confounding factor, per our studies in diseased and healthy older adults. Participants will also complete the Advanced Short Performance Physical Battery (SPPB-A) to assess mobility function. The SPPB-A includes timed measures of walking, static and dynamic balance assessments (including single leg), and repeated chair stands. As one leg is undergoing RT and the other PT, single leg balance assessments will be performed for each leg to examine differences in RT and PT, as it has been shown to increase with RT. A single-step test (SST), which correlates well with other lower limb functional performance measures, will also be performed on each leg. To perform the SST, volunteers stand on one leg (test leg) on a 15 cm high, single step and must touch the ground with their contralateral leg by performing a squat with the test leg and return to the standing position. The time required to repeat this movement 20 times is recorded. The non-test leg is held straight by a knee immobilizer brace.

Whole skeletal muscle function: Knee extensor (KE) peak torques for each leg will be measured on an isokinetic dynamometer (Biodex System 4) during maximal voluntary contractions at 0, 60, 120, 180, 240, 300 and 500°s⁻¹. Range of motion will be 70°, beginning at 80° of flexion, with 2 repetitions per velocity. Maximal contractile velocity will be obtained from the 500°s⁻¹ trial. Coin toss will determine which leg is tested first, and the order of contraction velocity will begin and end with 120°s⁻¹, to evaluate whether fatigue occurred, with the remainder of the contractions performed in random order. Motor point stimulation will be applied to the resting muscle to determine maximal rates of torque development (RFD_{stim}) and relaxation (RFR_{stim}) at 0°s⁻¹. In addition to quantifying intrinsic whole-muscle contractile properties, these values will be compared with the rates during ballistic, maximal voluntary contractions (RFD_{vol},

RFR_{vol}), to quantify differences in neural drive. An increase in the RFD_{vol}:RFD_{stim} ratio indicates increased contractile speed due to factors proximal to the point of stimulation.

Electromyography (EMG) measures of muscle activation (amplitude, timing of burst) will be obtained during all voluntary contractions. All torque data will be expressed relative to KE fat-free muscle mass, quantified by MRI, and MRI measures will be used to evaluate fat content and distribution.

Skeletal muscle biopsy: A percutaneous biopsy of the vastus lateralis will be performed following an overnight fast. The majority of tissue will be immediately placed into cold (4°C) dissecting solution, dissected into bundles, tied to glass rods and processed for single fiber contractile and mechanical assessment with the remainder either prepared for immunohistochemistry or frozen in liquid nitrogen and stored at -80°C.

Muscle fiber contractile and mechanical function: Single chemically-skinned skeletal muscle fibers will be prepared for sinusoidal analysis or specific force-velocity-power experiments. Fiber mechanics and steps in the cross-bridge cycle will be obtained using sinusoidal analysis, a technique first applied to human skeletal muscle by our laboratories. Fiber mechanics results include myofilament stiffness (A-elastic), the number of myosin heads strongly-bound to actin, the cross-bridge stiffness and myosin-actin cross-bridge kinetics. Cross-bridge kinetics measurements include the rate of myosin force production, or the rate of myosin transition between the weakly- and strongly-bound states, and the average myosin attachment time (t_{on}) to actin. Specific force and velocity will be measured using a force clamp technique. These measurements will be performed primarily on MHC I and IIA fibers, as these are the most abundant fiber types. Hybrid fibers (ie, MHC I/IIA) will be analyzed if enough are available.

Resistance exercise training. Our overall approach to RT and PT training is based on studies, as well as our preliminary work, that have demonstrated improvements in whole muscle and single fiber function are apparent within 16 wks or less. After recovery from the baseline biopsy (~1 wk), volunteers will begin a 16 wk, facility-based, resistance exercise training program (3 times/wk). Volunteers will have their dominant or non-dominant leg randomly assigned to RT with the contralateral leg assigned to PT (1:1 allocation). The training program will include: 1) leg press; 2) knee extension; and 3) knee flexion. Each exercise will be performed for RT for one leg and then for PT in the other leg before moving on to the next exercise. Prior to and at the end of each exercise session, volunteers will warm-up/cool-down on an exercise bike (~30-50 W) for 5 min. Based upon the National Strength and Conditioning Association guidelines and our resistance training of older adults, we expect the exercise session during to be less than one hour. Patients will be required to complete at least 90% or greater of the prescribed sets and 80% of the training sessions over the 16 wk period to be included in the analyses.

Low-velocity, high-load resistance training (RT): The intensity of the RT program will be 80% of one repetition maximum (1RM) for 3 sets of 8 repetitions, as recommended for maximum strength gains and as previously performed by our laboratories. Concentric and eccentric contraction phases for RT will last 2-3 sec. Exercise intensity for RT will progress over the first 3 weeks, as we have previously done. The first week will be 50% 1RM for 1 set of 10 repetitions, second week will be 60% 1RM for 2 sets of 8 repetitions and the third week will be 70% 1RM for 3 sets of eight repetitions. 1RM will be updated bi-weekly.

High-velocity, low-load power training (PT): The intensity of the PT program will be 40% 1RM for 3 sets of 16 repetitions. The PT program will be performed at 40% 1RM, instead of the 80% 1RM in the RT program, in order to increase the contractile speed during training and maximize the potential to improve whole muscle performance. The ability of 40% 1RM to better ameliorate age-related decreases in whole muscle performance is based upon the findings that power

output at 40% 1RM is a stronger predictor of ability to perform activities of daily living in both men and women than 1RM or 70% 1RM and contractile speed accounts for more of the decrease in functional performance than force decrements in older adults, especially in women. As PT improves the magnitude of muscle power output in older adults similarly from 20% to 80% 1RM, the main difference between a 40% and 80% 1RM should be the increased training contractile velocity that will occur with a reduced load. Notably, repetitions will be doubled with PT to equate to the total work performed with RT such that the two training programs will be equivalent. Concentric contraction phases for PT will be as quick as possible (~1 sec) with eccentric contractions lasting 2-3 sec. Exercise intensity for PT will progress over the first 3 weeks by increasing set and repetitions as the load will be set at 40% 1RM. The first week will be 1 set of 12 repetitions, second week will be 2 sets of 12 repetitions, and the third week will be 3 sets of 14 repetitions. 1RM will be updated bi-weekly.

Post-exercise testing. Post-exercise testing will include the same assessments of body composition, physical activity, whole skeletal muscle function as well as cellular and molecular structure and function as the pre-exercise testing listed above. Assessments will be made >5 days from the last whole muscle training session to eliminate residual exercise effects on fiber structure and function.

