Cover Page for ClinicalTrials.gov

Official Title of the Study:

Sex-specific Adaptation to Different Resistance Exercise Programs in Older Adults

Date of the document:

April 22, 2019

Our goal is to assess the main effects of training (traditional low-velocity, high-load resistance training and high-velocity, low-load power training versus baseline) and sex and determine if training alters muscle function differently in men and women (training by sex interaction). Primary outcomes include: (1) whole muscle: peak isometric torque and isokinetic power; (2) cellular: single fiber specific force, velocity, power; (3) molecular: myofilament stiffness (A-elastic), myosin rate of force production, myosin attachment time (t_{on}). We will model the data from this project with linear mixed models. This class of models is appropriate since it models the intra-participant correlation that is anticipated to result from the repeated measurements on each person, both multiple fibers and training protocols. This model and associated testing procedures such as likelihood ratio tests and large sample confidence intervals for coefficient contrasts will allow us to assess the main effects (treatment effects and sex effects) and their interactions. It also can accommodate other covariates, such as muscle size, if necessary. The analyses will be done in R and will use the lme4 library for linear mixed models. Transformations to normality, adjustments for multiple testing, and assessments of the linear assumptions will be done as appropriate. Additionally, we will examine correlations among functional parameters at different anatomic levels to determine whether cellular and molecular phenotypes relate to whole muscle parameters.

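### Leg dominance is left out of the named model and leg assignment has no stated balance by sex, which costs precision on the training-by-sex interaction and leaves it open to an unlucky draw

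*Protocol*

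**What the plan says.** **Allocation.** The Protocol (Methods, Resistance exercise training) states: "Volunteers will have their dominant or non-dominant leg randomly assigned to RT with the contralateral leg assigned to PT (1:1 allocation". It does not say whether the randomisation is simple, blocked or stratified, and it does not mention sex.

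**Target and model.** The SAP sets out to "determine if training alters muscle function differently in men and women (training by sex interaction". On method it says "We will model the data from this project with linear mixed models", naming training, sex and their interaction. It gives no model formula. On further terms it says only: "It also can accommodate other covariates, such as muscle size, if necessary". Dominance is neither named nor excluded.

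**Pairing.** The Protocol (Design) relies on both programmes being trained in the same person: "This within subject, unilateral training design provides a powerful model to evaluate training differences by reducing between-subject variability".

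**Baselines.** Torque is measured leg by leg (Protocol, Whole skeletal muscle function: "Knee extensor (KE) peak torques for each leg will be measured on an isokinetic dynamometer (Biodex System 4") and then scaled: "All torque data will be expressed relative to KE fat-free muscle mass, quantified by MRI". For tissue, the Protocol (Skeletal muscle biopsy) says "A percutaneous biopsy of the vastus lateralis will be performed following an overnight fast", without saying which leg is sampled or whether both are. The SAP compares the two programmes with baseline but does not say whether that baseline belongs to the leg.

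**The concern.** RT versus PT is a comparison between two legs of one person. Pairing removes differences between people but not differences between the legs. Dominance is the leg attribute on which the plan randomises, yet the analysis does not name it.

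The interaction compares the RT-minus-PT contrast in men with that in women. If RT falls on the dominant leg more often in one sex than in the other, any dominance difference enters the observed interaction. A 1:1 ratio kept overall but not within sex does not prevent this, because an excess in men is then mirrored by a deficit in women.

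At stake are the precision of a stated goal of the trial and the credibility of one realised result. A single allocation feeds all eight primary outcomes, so multiplicity adjustment does not address it.

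**Working it through.** The plan gives no sample size, SD, effect size or alpha, so there is no figure of its own to reproduce. Assumed: 10, 20 or 30 participants per sex; two-sided alpha 0.05; d/sigma of 0.25, 0.5 or 1; simple randomisation unless stated.

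**1. Set-up.** Let d be the dominant-minus-non-dominant difference between legs on the analysed scale. A participant's RT-minus-PT contrast is the training effect for that sex, plus d if RT is on the dominant leg or minus d if it is not, plus error with SD sigma. With share p on the dominant leg, the mean contrast in a sex moves by d(2p-1). The interaction therefore moves by d(2pM-1) - d(2pF-1) = 2d(pM-pF).

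**2. Size of the chance imbalance.** SD of pM-pF = sqrt(0.5/n), with n per sex; exact binomial probabilities.

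| n per sex | SD of pM-pF | Chance of 30 points or more | SD of shift, 2d x SD |
|---|---|---|---|
| 10 | 0.22 | 26% | 0.45d |
| 20 | 0.16 | 8% | 0.32d |
| 30 | 0.13 | 3% | 0.26d |

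A 30-point imbalance shifts the interaction by 2 x 0.3 x d = 0.6d. At an assumed d of 5% of the outcome that is 3 percentage points; at 10% it is 6. Balancing overall but not by sex leaves nearly the same SDs: 0.23, 0.16 and 0.13.

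**3. Average behaviour.** In 40,000 simulated trials per scenario without a dominance term, the mean shift lay between -0.002 and 0.003 (sigma = 1) and type I error between 0.048 and 0.052.

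**4. Precision.** Random plus-or-minus d adds d^2 to the contrast variance sigma^2, a ratio of 1+(d/sigma)^2:
- d/sigma 0.25: 1 + 0.0625, about 6% more
- d/sigma 0.5: 1 + 0.25, 25% more
- d/sigma 1: 1 + 1, 100% more

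**5. Given an unlucky draw.** Type I error when the realised imbalance is 30 points or more, without the term:

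| d/sigma | n=10 | n=20 | n=30 |
|---|---|---|---|
| 0.25 | 6.6% | 7.9% | 8.9% |
| 0.5 | 8.9% | 13.8% | 18.8% |
| 1 | 14.5% | 29.8% | 40.3% |

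With the term it is 4.5% to 5.6% throughout.

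**6. What each remedy buys.** Simulated power for a true interaction of (1.96+0.84) x sigma x sqrt(2/n):

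| d/sigma | n per sex | No term | Term | Term and sex-stratified |
|---|---|---|---|---|
| 0.5 | 10 | 66.1% | 73.1% | 75.5% |
| 0.5 | 20 | 68.6% | 76.5% | 77.9% |
| 0.5 | 30 | 69.2% | 78.2% | 78.8% |
| 0.25 | 10 | 73.0% | 72.9% | 75.2% |
| 0.25 | 20 | 75.3% | 76.4% | 77.9% |
| 0.25 | 30 | 75.7% | 77.8% | 78.7% |

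At 0.5 the term supplies 7.0 to 9.0 points and stratification a further 0.6 to 2.4. At 0.25 the total gain is 2 to 3 points, and at 10 per sex it comes from stratification rather than from the term.

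**The case against.** **Silence is not a statement.** The documents do not say that allocation ignores sex or that dominance is excluded. The method is unstated, and covariates are allowed if needed. This stands: the point is that neither safeguard is specified. Choosing covariates as needed also leaves the choice open until the data are seen.

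**Chance imbalance is not bias.** A reader might infer that the interaction is biased or its test invalid. Step 3 shows otherwise: over randomisations the shift averages zero, and the usual interval already carries this variation. Only inference conditional on a bad draw misleads.

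**Baselines and scaling may remove much of it.** This stands in part. Torque is measured on each leg and divided by fat-free muscle mass. If the analysis uses each leg's own baseline, a fixed difference in level cancels for torque and power, leaving only a dominance difference in training response. A reader might take the SAP to pool baseline across legs, but its goal statement does not say so. For the six cellular and molecular outcomes, cancellation needs a baseline biopsy from each leg, which the text leaves open. On the other hand, nothing in the documents suggests how large a dominance difference in these outcomes would be.

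**Large shifts are uncommon.** Splits of 70:30 or worse in at least one sex have a 57% chance at 10 per sex and 22% at 15 or 20. A reader might pair those figures with a shift of 0.8d (4 to 8 points at an assumed d of 5 to 10%). That size needs the sexes to differ by 40 points. Opposite 70:30-or-worse splits have a chance of 2 x 0.172^2 = 5.9% at 10 per sex and 0.7% at 15 or 20. Counting every split that differs by 40 points or more gives 11.5%, 4.3% and 1.7%. With exact overall balance at 10 per sex it is 18%. These figures also allow no cancellation by per-leg baselines.

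**Conclusion.** The point holds as one of precision and prespecification, not of validity. The plan states no sex-balanced leg assignment and names no dominance term, while making the training-by-sex interaction a goal.

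The loss is small if dominance matters little (interaction variance up about 6% at d/sigma 0.25) and worth recovering if it matters moderately (25% at 0.5, roughly 9 to 10 power points with both remedies). All sizes rest on assumed d, sigma and n, and the imbalance probabilities on simple randomisation.

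The concern is smallest for torque and power if per-leg baselines are used. It is largest for fiber and molecular outcomes if only one leg is biopsied at baseline. The documents do not support a reading that the interaction estimate is biased or its overall type I error inflated.

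**What to change.** - **Model.** Prespecify leg dominance as a fixed effect in every primary mixed model, with leg-specific baselines where measured. In a change-score or baseline-adjusted model this is one coefficient. If baseline and post-training values are both outcomes, add dominance by time, since a level term alone does not adjust the training response.
- **Allocation.** State the randomisation method and assign legs in permuted blocks separately for men and women. Keep the model term as well: exclusion for low adherence can undo the balance, and balance without the term leaves dominance variance in the residual.
- **Biopsy.** State which leg or legs are sampled at baseline. If only one, balance dominant against non-dominant, and RT against PT leg, within sex.

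**Cost.** One extra randomisation list and one model degree of freedom (two with the time interaction); no added participants or procedures. If allocation is already complete, the model term alone gives most of the gain wherever dominance matters enough to be worth adjusting for.

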Cover Page for ClinicalTrials.gov

Official Title of the Study:

Sex-specific Adaptation to Different Resistance Exercise Programs in Older Adults

Date of the document:

April 22, 2019

Our goal is to assess the main effects of training (traditional low-velocity, high-load resistance training and high-velocity, low-load power training versus baseline) and sex and determine if training alters muscle function differently in men and women (training by sex interaction). Primary outcomes include: (1) whole muscle: peak isometric torque and isokinetic power; (2) cellular: single fiber specific force, velocity, power; (3) molecular: myofilament stiffness (A-elastic), myosin rate of force production, myosin attachment time (t_{on}). We will model the data from this project with linear mixed models. This class of models is appropriate since it models the intra-participant correlation that is anticipated to result from the repeated measurements on each person, both multiple fibers and training protocols. This model and associated testing procedures such as likelihood ratio tests and large sample confidence intervals for coefficient contrasts will allow us to assess the main effects (treatment effects and sex effects) and their interactions. It also can accommodate other covariates, such as muscle size, if necessary. The analyses will be done in R and will use the lme4 library for linear mixed models. Transformations to normality, adjustments for multiple testing, and assessments of the linear assumptions will be done as appropriate. Additionally, we will examine correlations among functional parameters at different anatomic levels to determine whether cellular and molecular phenotypes relate to whole muscle parameters.

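### The SAP names no leg-level term or leg-baseline covariate, so, fitted as described, the RT-versus-PT comparison of torque and power gives each leg's measured baseline no weight

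*SAP*

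**What the plan says.** The SAP's goal sentence makes training a factor with baseline as the reference state: "main effects of training (traditional low-velocity, high-load resistance training and high-velocity, low-load power training versus baseline". The whole-muscle primary outcomes are "whole muscle: peak isometric torque and isokinetic power". The mixed model is justified because "it models the intra-participant correlation that is anticipated to result from the repeated measurements on each person, both multiple fibers and training protocols". On covariates the SAP says only: "It also can accommodate other covariates, such as muscle size, if necessary". It gives no model formula and no list of random effects. Neither leg nor leg baseline is mentioned.

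The Protocol, under Resistance exercise training, randomises legs within person: "Volunteers will have their dominant or non-dominant leg randomly assigned to RT with the contralateral leg assigned to PT (1:1 allocation". Under Whole skeletal muscle function, "Knee extensor (KE) peak torques for each leg will be measured on an isokinetic dynamometer", and under Post-exercise testing, "Post-exercise testing will include the same assessments of body composition, physical activity, whole skeletal muscle function". Each participant therefore supplies four values per torque or power outcome: two legs at two visits. The Objectives section makes RT versus PT, by sex, the purpose of the trial.

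**The concern.** RT versus PT is the only randomised contrast in the trial. Using both legs of one person removes between-person variance from it. It does not remove stable differences between that person's legs, which the trial also measures, at baseline. An analysis with no link between a leg's baseline and its own post-training value cannot use that measurement.

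Precision of RT minus PT, and of its interaction with sex, is at stake. So is the reported standard error, because a single residual variance has to stand in for leg asymmetry, visit-to-visit variation and measurement error together.

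**Working it through.** The documents give no sample size, SD, correlation, alpha or power, so there is no planned figure to reproduce. All variances, correlations and sample sizes below are assumptions.

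**Set-up.** Value = training mean + participant effect + leg effect (variance L) + participant-by-visit effect (variance V) + error (variance E). The participant and visit effects cancel from the between-leg difference at one visit. The correlation of the baseline and post-training between-leg differences is then rho = L/(L + E). More generally rho = (r1 − r3)/(1 − r2), with r1 the same-leg pre-post correlation, r2 the between-leg same-visit correlation and r3 the between-leg cross-visit correlation. It is not the raw pre-post correlation.

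**Step 1: what the estimate uses.** Generalised least squares weights for RT minus PT on (baseline of RT leg, baseline of PT leg, post RT, post PT), with training levels baseline, RT and PT throughout:

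| Random effects | Weights |
|---|---|
| Participant only | (0, 0, 1, −1) at every rho |
| Participant, leg, participant-by-visit | (−rho, +rho, 1, −1) |

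The second row has the same weights as ANCOVA on the leg difference. Baseline is a factor level in both rows; only the random effects differ.

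**Step 2: precision.** Variance with the leg baseline ÷ variance without = 1 − rho².

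| rho | 1 − rho² | Variance cut | SE without ÷ SE with |
|---|---|---|---|
| 0 | 1.00 | 0% | 1.00 |
| 0.3 | 0.91 | 9% | 1.05 |
| 0.4 | 0.84 | 16% | 1.09 |
| 0.6 | 0.64 | 36% | 1.25 |
| 0.8 | 0.36 | 64% | 1.67 |

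Power depends on where 80% is anchored (two-sided 0.05, so 2.80 standard errors). If the adjusted contrast has 80%, the unadjusted has Φ(2.80√(1 − rho²) − 1.96): 76%, 73%, 61% and 39% at rho 0.3, 0.4, 0.6 and 0.8. If the unadjusted contrast has 80%, the adjusted has Φ(2.80/√(1 − rho²) − 1.96): 84%, 86%, 94% and 99.7%. The documents support neither anchor.

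**Step 3: the standard error.** Under participant-only clustering, the residual variance averages three within-person contrasts: the two between-leg differences, each L + E on the residual scale, and the visit difference, 2V + E. The average is E + 2(L + V)/3, but RT minus PT needs L + E. The ratio of reported to true variance is

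k = [E + 2(L + V)/3] / (L + E).

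k is 1 only when V = L/2; a smaller V makes the standard error too small and a larger V too large. The large-sample null rejection rate of a nominal 5% test is 2Φ(−1.96√k). The last two columns are simulated at n = 30, 20,000 runs per setting.

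| L, V, E | k | Formula | Participant-only | Baseline-difference ANCOVA |
|---|---|---|---|---|
| 0.5, 0, 0.5 | 0.83 | 7.4% | 7.6% | 5.0% |
| 0.8, 0, 0.2 | 0.73 | 9.3% | 9.6% | 5.0% |
| 0.3, 0.5, 0.3 | 1.39 | 2.1% | 2.4% | 4.7% |
| 0.2, 0.6, 0.4 | 1.56 | 1.5% | 1.7% | 5.0% |

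**Step 4: is a leg effect alone enough?** No. With n = 40, V = 0.3 and L + E = 1 (150 simulated trials), mean reported standard errors at rho 0.5 were 0.227 for participant-only, 0.226 with a leg effect added and 0.197 for ANCOVA. At rho 0.8 they were 0.197 with the leg effect and 0.134 for ANCOVA. Without the participant-by-visit term, visit variation stays in the residual.

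**The case against.** The strongest reply is that the SAP has not committed to a participant intercept alone. It lists no random effects, allows further covariates and refers to correlation from training protocols; since each protocol is one leg, a protocol-within-person term might serve as a leg term. That stands as a caution: participant-only clustering is the natural reading, not the only one. But a random effect for participant by training state would not repair the model. Both baseline legs carry the same state, so nothing ties either to its own post-training value. The link appears only if leg is identified at both visits, which the SAP does not say.

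The size is also open to challenge. The paired design has already removed between-person variance. The protocol expresses torque relative to knee extensor fat-free muscle mass, which may remove some asymmetry. If rho is near zero, almost nothing is lost. All of this is right and is why the range must start at zero.

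A reader might infer that coding baseline as a level of the training factor is itself the error. Step 1 rules that out: the same coding with leg and participant-by-visit effects recovers the ANCOVA weights.

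**Conclusion.** The point holds as a gap in the leg-level structure for peak isometric torque and isokinetic power. Under the only clustering the SAP names, RT minus PT ignores a baseline that the trial collects. The variance penalty runs from nothing at rho 0 to a factor of 1/0.36 = 2.8 at rho 0.8. The reported standard error is right only if the participant-by-visit variance happens to be half the leg variance. In the settings tried, null rejection ran from about 2% to 9% by the formula, and from 1.7% to 9.6% in the simulation at n = 30.

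Two stronger readings are not supported. A reader might infer that the RT-versus-PT estimate is biased; legs are randomised, so it is not. A reader might also infer that the trial forfeits a known, large share of its power; the documents give no correlation, variance or sample size from which to say so. The 1 − rho² result assumes equal between-leg variance at the two visits for the mixed model; the ANCOVA form does not need that.

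**What to change.** Keep the SAP's mixed model for training versus baseline and for the sex effects. For leg-level outcomes, write its random effects out as participant, leg within participant, and participant by visit, with leg identified at both visits. Name RT minus PT and its interaction with sex as contrasts.

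For those two contrasts, either use that model or add one regression per outcome: each person's post-training RT-leg minus PT-leg difference on the same person's baseline difference and sex. Code sex as ±½ and leave the baseline difference uncentred. The intercept is then RT minus PT at equal sex weights for legs with equal baselines, and the sex coefficient is the interaction. Centring the baseline difference on its sample mean would put the observed baseline imbalance back into the intercept. The regression supplements the mixed model, since it cannot estimate training versus baseline or the sex main effect. A leg effect without the participant-by-visit term is not an equivalent substitute.

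The cost is SAP wording, a few lines of R and, for the regression, one degree of freedom. No new data are needed.

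### The SAP's training-versus-baseline effects on voluntary torque and power are uncontrolled 16-week changes and cannot be separated from test practice or time

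*SAP*

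**What the plan says.** The Design section has "healthy, sedentary older (65-75 years old) men and women exercise one leg using RT and the contralateral leg using PT". Legs are allocated within person: "Volunteers will have their dominant or non-dominant leg randomly assigned to RT with the contralateral leg assigned to PT (1:1 allocation"). The same section remarks that "Unilateral exercise, with one leg exercised and the other as a control, has been commonly used in older populations", but this trial keeps no such control leg.

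On timing, the Methods say: "Baseline testing will occur prior to exercise and include assessments of body composition, physical activity, and whole skeletal muscle" and go on to cellular and molecular function. The tests are repeated after 16 weeks. No familiarisation session, repeat baseline or untrained period is mentioned.

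Under Whole skeletal muscle function, knee-extensor torque is measured "during maximal voluntary contractions at 0, 60, 120, 180, 240, 300 and 500°s⁻¹", "beginning at 80° of flexion, with 2 repetitions per velocity". The 120°/s contraction is done first and last in the session as a check on fatigue. Motor point stimulation and EMG are also planned.

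The SAP lists eight primary outcomes: two whole-muscle (peak isometric torque, isokinetic power), three single-fibre and three molecular. It defines the training main effect as RT and PT against baseline, and sets out to "determine if training alters muscle function differently in men and women (training by sex interaction"). It has no term, caveat or sensitivity analysis for practice or time.

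**The concern.** A maximal voluntary test measures both the muscle and the volunteer's skill and confidence with the test. Sedentary people aged 65 to 75 may well perform below their maximum at a first dynamometer test. If so, a second test would be higher even without training. Four months also pass between tests, during which season, equipment or operators may change.

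With both legs trained and no untrained comparison, nothing in the design estimates that component. The SAP nevertheless calls the whole change a training effect. Torque is also divided by fat-free muscle mass. That removes gain proportional to muscle growth but leaves practice in, so practice can be a larger share of what is reported.

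What is at stake is the claim that either program improves torque or power by a stated amount and, under a further condition, the claim that men and women respond differently relative to baseline.

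**Working it through.** The documents state no sample size, SD, effect size or alpha, so there is no figure of theirs to reproduce. The check is contrast algebra, then illustrative sizes under stated assumptions.

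**Inputs from the documents.** Three conditions (baseline, RT, PT) in each sex; both legs trained; 16 weeks; two voluntary primary outcomes out of 2 + 3 + 3 = 8.

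**Step 1: what each contrast contains.** For sex s, let the true training effects be τ(RT,s) and τ(PT,s). Let p(s) be the practice-plus-time gain, equal in the two legs. Write τ̄ for the average over RT and PT.

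- Main effect versus baseline = mean τ̄ + [p(men) + p(women)]/2
- Versus-baseline training by sex = [τ̄(men) − τ̄(women)] + [p(men) − p(women)]
- RT minus PT = τ(RT) − τ(PT); p cancels
- RT minus PT by sex: p cancels

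Set every τ to zero, with practice in arbitrary units:

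| p(men), p(women) | Main effect | Training by sex | RT − PT | RT − PT by sex |
|---|---|---|---|---|
| 5, 5 | 5.0 | 0 | 0 | 0 |
| 5, 8 | (5 + 8)/2 = 6.5 | 5 − 8 = −3.0 | 0 | 0 |

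The main effect takes in the full average practice gain. The interaction takes in only the sex difference in practice.

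**Step 2: error rates.** Assumptions: n = 10 to 25 per sex, two-sided 5% test, normal approximation, practice d in SDs of participant-level change (legs averaged), no true effect. The rejection rate is 1 − Φ(1.96 − d/SE) + Φ(−1.96 − d/SE), with SE = 1/√(2n) for the main effect and √(2/n) for the interaction. In the main-effect row d is a common practice gain; in the interaction row it is the sex difference in practice.

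| | d = 0 | d = 0.2 | d = 0.3 |
|---|---|---|---|
| Main effect | 5.0% | 14.5% to 29.3% | 26.9% to 56.4% |
| Interaction | 5.0% | 7.3% to 10.9% | 10.3% to 18.6% |

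Example, main effect with n = 10 and d = 0.2: SE = 1/√20 = 0.224, d/SE = 0.894, rate 14.5%. Practice common to both sexes, whatever its size, leaves the interaction at 5.0%.

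**Step 3: size of overstatement.** Reported gain = true gain + practice. With an assumed true gain of 15% and practice of 3% to 10%, the report is 18% to 25%, too large by 3/15 = 20% to 10/15 = 67%. The ratio depends on the assumed gain: at 7.5% it is 40% to 133%, at 30% it is 10% to 33%. For the interaction with equal true gains, equal practice gives 0; practice of 4% in one sex and 8% in the other gives 4 points, or 4/15 = 27% of a 15% gain.

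**Step 4: proportional practice.** If both sexes gain the same percentage q, and the men:women baseline ratio is r, the raw-scale interaction is q(r − 1) of the women's baseline. For q = 5% and r = 1.0 to 1.5 (assumed), that is 0% to 2.5%. For q = 3% to 10% at r = 1.5, it is 1.5% to 5.0%. On the log scale it is 0.

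**The case against.** The strongest reply is that the comparison named in the Objectives is RT against PT by sex. Legs are randomised, and practice equal in the two legs drops out of that comparison. This stands. So does the fact that six of the eight primary outcomes are measured on biopsy fibres, which rehearsal of a voluntary test cannot change.

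A second reply is that better muscle activation after 3 × 16 = 48 scheduled sessions, which include knee extension, is part of the training effect. That also stands. The artefact is the gain that would have appeared on retest without training, plus any drift over time, and it may be small after four months. The difficulty is that the design cannot show how small.

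Third, the protocol has stimulated rates of torque development and relaxation, the voluntary-to-stimulated ratio, and EMG. These help separate neural from muscular change. They cannot separate learning the test from neural adaptation to training, because both would raise the ratio, and they are equally uncontrolled for time. The repeated 120°/s contraction addresses fatigue within a session only.

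Fourth, the absence of familiarisation is inferred from silence in a short document. It may be done and not written down. If so, most of the practice concern falls away, but the time component remains.

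A reader might infer that the training-by-sex test necessarily contains practice, so that the trial's central question is compromised. The documents do not support this. Equal practice cancels in that interaction on an additive scale, and nothing in either document indicates that men and women differ in practice, or excludes it.

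**Conclusion.** The point holds for the two voluntary primary outcomes and for the versus-baseline main effects. As planned, RT-versus-baseline and PT-versus-baseline changes in torque and power are uncontrolled pre-post differences. For their sex interaction, bias is possible but conditional on a sex difference in practice, or on proportional practice with unequal baselines on a raw scale.

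The direction is clear for a positive practice gain: the versus-baseline effects are inflated. The size is unknown. Every percentage, SD-unit and sample-size value in the calculations is an assumption. The protection of RT minus PT rests on practice being equal in the two legs. Randomised leg assignment and the coin toss for which leg is tested first make that reasonable.

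This is a cheap improvement to interpretation and baseline testing. It does not invalidate the design.

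**What to change.** 1. In the SAP, name RT minus PT, and RT minus PT by sex, as the contrasts that support causal conclusions. Report versus-baseline torque and power as uncontrolled 16-week change. State that their sex interaction assumes equal practice in men and women, and on which scale (raw or log). Use the stimulated measures and EMG as supporting evidence. Do not require them to agree in direction, because such a rule could disallow a real neural gain. This costs wording only and can still be done after data collection.

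2. In the protocol, state whether familiarisation is done. If it is not, and baseline testing is still open, run one unscored series of the dynamometer test on each leg before the scored baseline. The cost is a little participant time and probably a smaller reported gain. This reduces practice but does nothing about time or laboratory drift, so item 1 is needed either way.
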